Date: 1 March 2020

Study Name: Comparison Of The Incidence Of Recurrent Laryngeal Injury Following The Dissection Of The Nerve By Cranio-Caudal And Lateral Approach By Using Introoperative Nerve Monitoring

Study Design: This prospective study was approved by the institutional review board and informed consent was obtained from each patient . A total of 327 patients who were referred to undergo thyroid surgery between June 2018 and November 2019 were assessed for the eligibility to participate in the study. Of these, 233 were considered to be eligible for the study. Exclusion criteria included previous thyroid or parathyroid surgery, substernal goiter, preoperative VCP, evidence of lateral lymph node metastasis, intentional transection of the RLN due to tumor invasion, failure to assess RLN functioning due to equipment issues with the IONM setup, presurgical dissection amplitude of $<500\mu\text{V}$ and patient's refusal to participate in the study. Of 327 patients, 94 were excluded preoperatively due to previous neck surgery (n=47), evidence of lateral neck metastasis(n=24), patient's refusal (n=13) and presence of substernal goiter (n=10). The remaining 233 patients were randomized to have RLN's identified by lateral (n=121) or cranio-caudal approach (n=112 (Figure 1). Computer generated random numbers were generated and printed on cards. These cards were placed in sealed, opaque envelopes. On the morning of operation, one envelope was opened before the operation and, depending of the parity of the number, RLN's of the patient were dissected either by cranio-caudal or lateral dissection during the operation. The patients and the nerves at risk (NAR's) in the lateral and cranio-caudal approach groups were classified as group 1 and 2, respectively. In group 1 and 2, nine and twenty-six patients were further excluded, respectively, owing to intraoperative failure to assess RLN functioning due to equipment issues with the IONM setup or presurgical dissection amplitude of $<500\mu\text{V}$.

Thus, the data of 198 patients were analysed for primary and secondary outcome measures. The primary endpoint was RLN injury and the secondary endpoints included the effect of clinicopathological features, anatomic variations and adverse EMG changes on the occurrence of RLN injury. Of 198 patients, 112 were in the lateral approach group (group 1) and 86 in the cranio-caudal approach group (group 2). Total thyroidectomy or lobectomy was

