performed in 158 (79.8%) and 40 (20.2%) patients, respectively. Sixteen (8%) patients underwent unilateral central lymph node dissection (CLND) additional to total thyroidectomy. Age, gender, body mass index (BMI), the indications for surgery, presence of hyperthyroidism, evidence of autoimmune thyroid disease (ATD) and thyroid lobe volume were recorded in all patients, preoperatively. Thyroid lobe volume was calculated by using the dimensions (length(L), width(W), thickness(T)) of each thyroid lobe measured by ultrasonography according to the following formula; $\pi/6 \times L \times W \times T^{18}$.

All NAR's were dissected by using CIONM including vagal response evaluation at the beginning and at the end of the operation (IONM = L1,V1, R1, R2,V2, L2) according to the recommendations by the International Intraoperative Neural Monitoring Study Group ⁷. All patients underwent pre-, and postoperative laryngoscopic examination within 2 days after surgery, and repeated serially if abnormal (L1, L2). All operations were performed by experienced endocrine surgeons. Length of RLN dissection was defined as extended if the nerve was dissected for 5 cm or greater. Duration of lobectomy for each site, period of time for initial identification of RLN after the mobilization of upper pole on each site, the relationship of the RLN to the ligament of Berry (LOB) and to the Tubercl of Zuckerkandl (TZ) (if present), extralaryngeal branching of the RLN, length of RLN dissection, presurgery and postsurgery amplitude and latency of the vagus and the RLN, occurrence of adverse EMG changes and recovery time or loss of signal (LOS) were recorded intraoperatively in all patients. Serum levels of calcium and parathormone on the first postoperative day were analyzed in all patients. The rates of post-thyroidectomy hypoparathyroidism and vocal cord palsy (VCP) were recorded. Final histopathological diagnosis was documented in all patients, postoperatively.

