Demographic data, BMI, the indications for surgery, clinicopathological features, thyroid volume, duration of the operation, period of time for RLN identification, anatomical variations, length of RLN dissection, presurgery and postsurgery amplitude and latency of the vagus and RLN, the rate of adverse EMG changes, LOS and morbidity (vocal cord palsy, hypoparathyroidism) were compared between group 1 and 2. The correlation between intraoperative adverse EMG changes and anatomic variations, lobe volume and type of thyroid disease was investigated as well.

Thyroid surgery and CIONM technique

All operations were performed under general anesthesia by using a small dose (0.3 mg/kg) of non-depolarizing muscle relaxant (Esmeron; MSD Sharp & Dohme GmbH, Haar, Germany) at intubation. The endotracheal tube was properly inserted to ensure that the recording surface electrode was placed at the level of the vocal cords. Prior to lobectomy, the carotid sheath was carefully dissected and the vagus nerve was identified using a hand held stimulation probe. The vagus nerve was dissected over a distance of ≤ 1 cm to place the vagus electrode. (automated periodic stimulation (APS) (Medtronic Xomed, Jacksonville, FL) or saxaphone probe (vagus electrode) ([name] GmbH, Avalanche SI, Germany).

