The baselines for latency and amplitude were automatically calibrated after the connection of the vagus electrode with the neuromonitoring system. CIONM had been carried out with one of the two following commercially available neuromonitoring devices: (1) NIM 3.0 Nerve Monitoring Systems; Medtronic Xomed, Jacksonville, FL; or (2) [name] GmbH, Avalanche SI, Germany. Achievement of initial presurgical dissection amplitude of $\geq 500\mu\text{V}$ was aimed in all patients. During the operations, adverse EMG parameters were defined as amplitude decrease of 50% or more of baseline value and/or latency increase of 10% or more ¹¹. A combined event (CE) was defined as concordant amplitude decrease of more than 50% and latency increase of more than 10%, regarding to baseline values ¹¹. The surgical maneuver was immediately altered and the traction released if adverse EMG changes were noted during surgery and waited to achieve the recovery of EMG changes. Recovery was defined as amplitude recovery to $>50\%$ of the initial baseline amplitude. Loss of signal (LOS) was defined as amplitude $<100\mu\text{V}$ ¹⁹. In case of LOS during the surgery of initial site, contralateral surgery was aborted if the amplitude did not recover to greater than 50% of the initial baseline amplitude within 20 minutes of the initial decline. During surgery, isthmus was divided first in both group of patients. Then the upper lobe of the gland was dissected through the avascular zone between the upper lobe and the cricothyroid muscle. The external branch of the superior laryngeal nerve was identified visually and, or by using neuro-monitoring hand probe prior to dissection of the upper pole vessels, and then the branches of upper pole vessels were ligated individually. Identification and preservation of all parathyroid glands and their vascular supply was tried in all cases. In case of incidental parathyroidectomy or totally compromised vascularity of the parathyroid glands, autotransplantation in to sternocleidomastoid muscle was performed.

RLN identification

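### Hypoparathyroidism and vocal cord palsy appear to be compared only in the 112 and 86 patients left after 9 and 26 randomised patients were removed for nerve-monitoring reasons, although neither outcome needs a nerve signal to be ascertained

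*Protocol*

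**What the plan says.** All places are in the Protocol, under Study Design, unless stated.

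- **Allocation.** 233 patients were randomised, 121 to lateral and 112 to cranio-caudal dissection. On the morning of surgery "one envelope was opened before the operation", and it fixed the approach.
- **Removal.** By arm, lateral first and then cranio-caudal: "nine and twenty-six patients were further excluded, respectively, owing to intraoperative failure to assess RLN functioning due to equipment issues with the IONM setup". The alternative reason was a presurgical amplitude below 500 microvolts. Both reasons are on the list of exclusion criteria. The two reasons are not split by arm.
- **Groups.** After these removals the text reads "Of 198 patients, 112 were in the lateral approach group (group 1) and 86 in the cranio-caudal approach group (group 2"). It ties the 198 to the primary and secondary outcome measures. Hypoparathyroidism is not among the endpoints it names.
- **Comparison.** "morbidity (vocal cord palsy, hypoparathyroidism) were compared between group 1 and 2".
- **Measurement.** "Serum levels of calcium and parathormone on the first postoperative day were analyzed in all patients". Vocal cord function was checked by "postoperative laryngoscopic examination within 2 days after surgery, and repeated serially if abnormal".
- **Analysis.** The SAP names a chi-square test for proportions and a 0.05 threshold. It defines no analysis set, and neither document describes an analysis of all randomised patients.

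**The concern.** The removals make sense for the EMG comparisons. Without a usable signal, an amplitude fall or a loss of signal cannot be scored. Hypoparathyroidism rests on blood results or clinical findings and vocal cord palsy on laryngoscopy. Neither needs a signal to be ascertained.

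The removals came after the envelope was opened, and they fell about three times as often on the cranio-caudal arm. A presurgical amplitude is measured before the approach is used, and an equipment fault should not depend on the approach, so the imbalance has no evident explanation. Listing an exclusion rule does not preserve the randomised comparison if the rule is applied once the arm is known. A chi-square test on the retained patients does not restore it.

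At stake is a between-arm safety statement, together with some precision that could be kept.

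**Working it through.** **1. Patient flow (Protocol, Study Design).** 327 − 94 = 233; 121 + 112 = 233; 121 − 9 = 112; 112 − 26 = 86; 112 + 86 = 198. The protocol's figures reproduce.

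**2. Removal by arm.**
- Lateral: 9/121 = 7.4%. Cranio-caudal: 26/112 = 23.2%. Overall: 35/233 = 15.0%.
- Difference 23.2 − 7.4 = 15.8 points (Newcombe 95% CI 6.6 to 25.1); ratio 3.1; Fisher exact p = 0.0009.

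**3. Precision.** At a common rate p, the standard error of the arm difference is √(p(1−p)) × √(1/n₁ + 1/n₂).
- Retained: √(1/112 + 1/86) = 0.1434.
- Randomised: √(1/121 + 1/112) = 0.1311.
- Ratio 1.093, so the interval is about 9% wider on the 198 at any common rate. Information lost: 1 − (0.1311/0.1434)² = 0.164, about 16%.

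The documents give no hypoparathyroidism rate, so the rates below are assumed. The half-width is 1.96 × √(p(1−p)) × factor.

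| Assumed rate | 198 patients | 233 patients |
|---|---|---|
| 5% | 6.1 points | 5.6 points |
| 10% | 8.4 | 7.7 |
| 20% | 11.2 | 10.3 |
| 30% | 12.9 | 11.8 |

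**4. Possible distortion.** The error in the retained-set difference (cranio-caudal minus lateral) is 0.2321 × g₂ − 0.0744 × g₁, where g is the retained minus the removed rate in each arm.
- Gap of 10 points in both arms: 2.32 − 0.74 = 1.6 points. Gap of 20 points in both: 3.2.
- Gap of 10 or 20 points in the cranio-caudal arm only: 2.3 or 4.6.
- A gap of opposite sign reverses the sign of the error.

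**5. Extreme bounds, starting from an assumed 22/112 vs 17/86 (about 20% each).**
- All 26 and none of the 9 are cases: 43/112 − 22/121 = +20.2 points.
- None of the 26 and all of the 9 are cases: 17/112 − 31/121 = −10.4 points.
- With 2 of the 9 lateral patients as cases (24/121), 18 of the 26 (69%) would have to be cases before the test reached p < 0.05. That is extreme.

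**6. A borderline result, assumed 22/112 vs 28/86 (chi-square without continuity correction, p = 0.038).** The removed lateral patients take their arm's rate (2 of 9, giving 24/121).
- Removed cranio-caudal patients at about the lateral rate (5 of 26): 33/112, p = 0.088.
- Removed cranio-caudal patients at about their own arm's rate (28/86 × 26 = 8.5, so 8 or 9 of 26): 36/112 or 37/112, p = 0.032 or 0.022.

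The same result weakens under one assumption and strengthens under the other.

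**The case against.** **The denominator is inferred.** A reader might take it that the plan states 112 vs 86 for hypoparathyroidism. It does not. The 198 are tied to the primary and secondary outcomes, the group labels are first used before the removals, and a count restricted to the 158 total thyroidectomies cannot be ruled out. The retained groups remain the most natural reading, since they are the only ones described as analysed.

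**Monitoring may matter for more than ascertainment.** A reader might infer that the reasons for removal have no bearing at all on hypoparathyroidism. The documents support that only for obtaining the result. Under Thyroid surgery and CIONM technique, an unrecovered loss of signal on the first side stops contralateral surgery. Under RLN identification, repeated or unrecovered EMG changes lead to conversion to another approach. Where monitoring failed, these rules may not have operated, so the extent of surgery may have differed. This argues for care in interpretation. It does not justify dropping the patients from the randomised comparison.

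**The results may not exist.** The protocol uses the same all-patients wording for intraoperative EMG recordings as for the blood tests. Usable EMG is unlikely after equipment failure, so the phrase may mean the 198. This stands as an open question, and the fix has to allow for it.

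**The effect is small and the outcome is minor.** This also stands. The interval widens by about 9%, the illustrated distortions are a few points, and hypoparathyroidism is neither the primary nor a listed secondary endpoint. The same removal matters more for the primary endpoint, RLN injury, so a change confined to hypoparathyroidism would be incomplete.

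**Conclusion.** The point holds as a modest improvement. On the natural reading of the groups, hypoparathyroidism is compared after 7.4% vs 23.2% of randomised patients were removed once allocation was known, for reasons that do not prevent it from being ascertained. The comparison is no longer the randomised one, and about 16% of the information is given up. The precision figures assume that all 35 removed patients have a result. The same reasoning extends to vocal cord palsy, which stands in the same sentence and is assessed by laryngoscopy. The patient-level precision figures carry over to it only if it is counted per patient and not per nerve.

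Two stronger conclusions are not supported:

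- A reader might infer that the comparison is biased towards one approach, or that a borderline finding would lose significance in the full set. With no rates in the documents, neither the direction nor the size of bias can be known, and step 6 shows that significance can move either way.
- A reader might treat the lack of a stated criterion as a second design fault. The protocol says only "The rates of post-thyroidectomy hypoparathyroidism and vocal cord palsy (VCP) were recorded", with no marker, threshold or day, whereas loss of signal has a numeric limit. That is a reporting gap and carries no weight in this conclusion.

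**What to change.** **Change.** Compare hypoparathyroidism as randomised, 121 vs 112, with the risk difference and 95% CI, and show the 198 as a sensitivity analysis. Report by arm how many of the 35 have no day-1 calcium or parathormone result, and give best-case and worst-case bounds for them. Do the same for vocal cord palsy, reporting how many of the 35 lack a postoperative laryngoscopy. Print the denominator for each outcome. The EMG comparisons can stay in the 198. One sentence stating the hypoparathyroidism criterion would close the reporting gap.

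**Cost.** If the results exist, the cost is one table row per outcome. If they do not, records must be searched, and the bounds may be wide: in step 5 they run from −10.4 to +20.2 points.

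**Downside.** Some of the 35 may not have received the assigned approach or the monitoring-driven conduct of surgery, and including them could dilute a true difference. Assume that all 9 removed lateral patients had lateral dissection and that k of the 26 switched to it. The full-set difference then shrinks by k/112, while the standard error shrinks by 1 − 0.1311/0.1434 = 8.5%. The break-even is 0.0855 × 112 = 9.6, so the gain in precision outweighs dilution for up to 9 switches. Beyond that the 198 would have more power, but they would still not be the randomised comparison.

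### Monitoring device and surgeon are in no list of variables or comparisons, and unequal exclusions after randomisation mean their balance cannot be assumed in the 198 patients analysed

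*Protocol*

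**What the plan says.** The protocol's section on thyroid surgery and CIONM technique says "CIONM had been carried out with one of the two following commercially available neuromonitoring devices". It names two manufacturers' systems, each with a different vagal electrode. It gives no rule for which patient was monitored with which system, and no counts by arm.

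On surgeons, the Study Design section says only "All operations were performed by experienced endocrine surgeons". Their number and their split by arm are not given.

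Two rules are set in absolute microvolts:
- "Achievement of initial presurgical dissection amplitude of" at least 500 µV was the aim in all patients, and the Study Design section excludes patients below that value.
- "Loss of signal (LOS) was defined as amplitude" below 100 µV.

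Other EMG criteria are relative to the patient's own baseline: "adverse EMG parameters were defined as amplitude decrease of 50% or more of baseline value and/or latency increase of 10% or more". Combined events and recovery are also defined against baseline.

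The list of intraoperative data ends with "occurrence of adverse EMG changes and recovery time or loss of signal (LOS) were recorded intraoperatively in all patients". Neither that list nor the list of between-group comparisons and correlations that follows includes device or surgeon. The secondary endpoints do not name them either.

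Allocation used random numbers in sealed, opaque envelopes, one opened on the morning of surgery: "depending of the parity of the number, RLN's of the patient were dissected either by cranio-caudal or lateral dissection". No stratification is described.

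The SAP compares continuous variables by t-test or Mann-Whitney test and proportions by chi-square. Only factors significant in univariate analysis go on to logistic regression.

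**The concern.** Raw amplitude and latency are compared between arms, and two decisions turn on fixed microvolt values. If the two systems give different readings for the same nerve, three things move with the device mix: the arm means, the loss-of-signal rate, and the set of patients who reach the analysis. Identification time and lobectomy duration could likewise move with the surgeon mix.

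In an intact randomised comparison this would mostly cost precision. Here the analysed set is not the randomised set. Patients left it after allocation for two reasons, both of which arise through the monitoring equipment, and they left the two arms at different rates. Device is an obvious variable with which to examine that difference, and the plan does not list it. Nor would the SAP bring it in. The continuous outcomes have no adjusted analysis, and a factor that is not listed for univariate testing has no planned route into the logistic model.

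**Working it through.** **1. Patient flow, from the Study Design section.** 47 + 24 + 13 + 10 = 94 excluded before allocation; 327 − 94 = 233; 121 + 112 = 233 randomised. After allocation, 121 − 9 = 112 and 112 − 26 = 86, total 198. The stated counts reproduce.

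**2. Exclusions after randomisation (equipment failure or amplitude below 500 µV).**
- Lateral: 9/121 = 7.4%. Cranio-caudal: 26/112 = 23.2%.
- Difference: 15.8 points.
- Standard error: √(0.232 × 0.768/112 + 0.074 × 0.926/121) = 0.046, so the 95% CI is 6.7 to 24.9 points.
- Fisher's exact p = 0.0009; chi-square p = 0.0008 (0.0015 with continuity correction).

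The documents do not split the 9 and the 26 by reason or by device.

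**3. Chance imbalance in device share among the randomised.** The device share f is not given, so 30% and 50% are assumed. The SD of the arm difference is √[f(1 − f)(1/121 + 1/112)], which is 6.0 points at f = 0.3 and 6.6 at f = 0.5. The 95% limits are about 12 and 13 points. This is ordinary sampling variation.

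**4. What the exclusions alone could do to device balance.** Suppose both arms start with the same share of device A and every exclusion falls on one device, an extreme case.
- f = 0.5, all on A: (60.5 − 9)/112 = 46.0% against (56 − 26)/86 = 34.9%, a gap of 11 points.
- f = 0.3, all on A: (36.3 − 9)/112 = 24.4% against (33.6 − 26)/86 = 8.8%, a gap of 16 points.
- f = 0.3, all on the other device: 36.3/112 = 32.4% against 33.6/86 = 39.1%, a gap of 7 points.

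If exclusions were unrelated to device, the expected gap is zero. So in this one-device scenario the range is 0 to about 16 points, and nothing planned would show where in it the trial lies.

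**5. Effect on outcomes, on assumed inputs.** The shift in an arm difference is the device-share gap times the device effect.
- Binary outcome such as loss of signal: gaps of 5 to 14 points and device effects of 3 to 10 points give 0.05 × 0.03 = 0.15 points up to 0.14 × 0.10 = 1.4 points.
- Mean amplitude: a 14-point gap and a device difference of 100 to 300 µV give 14 to 42 µV. The documents give neither a device difference nor an amplitude SD, so this cannot be called large or small.

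**6. Could device mix by itself explain the exclusion gap?** If one system lost 5% of patients and the other 25%, the arms' device shares would have to differ by 0.158/0.20 = 79 points. With 5% and 40%, 0.158/0.35 = 45 points. Both are far beyond the chance limits in step 3. At these assumed rates, chance imbalance in device is not a likely explanation for the gap.

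**The case against.** The strongest reply is that allocation was random and concealed. Simple randomisation balances unlisted factors in expectation, and an unadjusted test already allows for chance imbalance in device or surgeon. Lack of stratification costs precision and does not create bias. That is correct for the 233 randomised. A reader might infer from the parity rule that nothing balanced these factors, or that any arm difference is confounded with them. The documents do not support either reading. The reply carries less weight for the 198 analysed, because the exclusions came after allocation and were unequal.

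Second, most EMG criteria protect themselves. Adverse change, combined event and recovery refer to the patient's own baseline, so a proportional difference between devices cancels. Vocal cord palsy was assessed by laryngoscopy, not by amplitude. This stands, and it confines the device question to raw amplitude and latency, loss of signal and the 500 µV exclusion. How far it reaches nerve injury cannot be settled, because the documents give no operational definition of that endpoint.

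Third, three further readings are tempting and go beyond the text:
- That device or operator was chosen to follow allocation, because the envelope was opened on the morning of surgery. The documents are silent on when either was fixed, and silence is not evidence that it happened.
- That device caused the 7.4% against 23.2% gap. No exclusion is reported by device, and step 6 of the working shows that an ordinary chance imbalance would not be enough at the assumed rates.
- That device and surgeon were never recorded. They are only absent from the lists and may well be in the operative notes.

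Finally, recruitment ended in November 2019 and both documents are dated March 2020, so any covariate added now is post hoc. That is true, and the adjusted analyses must carry that label.

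**Conclusion.** The point holds in a limited form. Two systems with different vagal electrodes and more than one surgeon were used. Neither factor is listed for recording or comparison, and the SAP has no adjusted analysis of continuous outcomes. This is not bias by design.

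The established quantity is the difference in exclusions after randomisation, 15.8 points (95% CI 6.7 to 24.9), for reasons that arise through the monitoring equipment. It means that balance of device or surgeon cannot be taken for granted in the 198 analysed. Any resulting shift in the outcomes is unknown. The illustrations of 0.15 to 1.4 points for a binary outcome and 14 to 42 µV for amplitude rest entirely on assumed device shares and device effects. The documents do not show that the two systems read differently or that results varied by surgeon. This is a modest improvement to the analysis and reporting, not a flaw that invalidates the comparison.

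**What to change.** - Take monitoring device and operating surgeon for each patient from the operative records.
- Tabulate both by arm for all 233 randomised patients, and show the 35 exclusions by arm, device and reason. A table of the 198 alone would hide the selection step.
- Adjust the between-arm comparisons of raw amplitude and latency for device, and loss of signal too if there are enough events. Adjust identification time and lobectomy duration for surgeon. Report these beside the unadjusted results and state that they were added after data collection.
- For nerve injury, show counts by arm within device and within surgeon, with no extra model terms.
- Note next to the adjusted results that adjustment can address a device imbalance among those analysed but does not undo the exclusions.

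The cost is two fields from records that should already exist, two tables and a few lines of SAP text. The downsides are some degrees of freedom, which cannot be counted because the number of surgeons is not given, and the post hoc status of the adjusted results.

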Lateral approach: Following the ligation of upper pole vessels, the thyroid lobe was pulled anteromedially and the RLN was seeked within the carotid triangle at the level of inferior thyroid artery (ITA). The tissue between the carotid artery and the trachea was dissected gently parallel to the direction of the nerve until the nerve is identified visually and by hand held stimulation probe. After the identification of RLN, the vessels of inferior thyroid lobe was ligated. The nerve was dissected along its course to the entry point, and then the thyroid lobe was totally dissected from the trachea and the lobectomy was completed. If adverse EMG changes were encountered during lateral approach, traction was released immediately and waited for recovery. If the adverse EMG changes recovered, RLN dissection was proceeded by lateral approach again. If the adverse EMG changes did not recover after traction release or in case of repeated adverse EMG changes, lateral approach was abandoned. The thyroid lobe was retracted laterally and medial aspect of the lobe was dissected from the trachea. The RLN dissection was continued by medial approach in such cases.

Cranio-caudal approach: Following the ligation of upper pole vesels, the upper pole was retracted antero-medially to expose crico-pharyngeal muscle. The RLN was identified at the point of entry both visually and with hand held stimulation probe. The RLN dissection was proceeded craniocaudally by the division of the suspensory ligaments of the LOB through the level of ITA. After the identification and visualization of the RLN through its whole course, the medial and inferior vessels of the thyroid gland were dissected and ligated. Then, the lobe was dissected from the trachea and lobectomy was completed. If adverse EMG changes were encountered during cranio-caudal approach, traction was released immediately and waited for recovery. The RLN dissection was proceeded by cranio-caudal fashion again if the EMG changes recovered. If the EMG changes did not recover or in case of repeated adverse EMG changes, cranio-caudal approach was abandoned and RLN was dissected by lateral approach. If repeated adverse EMG changes were encountered despite conversion from cranio-caudal to lateral approach, then the lobe was retracted laterally and medial aspect of the lobe was dissected from the trachea. The RLN was dissected by medial approach in such cases with repeated adverse EMG changes.

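### Does an amplitude-only definition of EMG recovery, when a latency rise alone counts as an adverse change, call for a change to the plan?

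*Protocol*

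**What the plan says.** The protocol section on thyroid surgery and CIONM technique sets the event definition: "adverse EMG parameters were defined as amplitude decrease of 50% or more of baseline value and/or latency increase of 10% or more". It defines the combined event separately ("A combined event (CE) was defined as concordant amplitude decrease of more than 50% and latency increase of more than 10" per cent), so events in a single parameter, including latency alone, are a class of their own. The same section then gives the recovery rule: "Recovery was defined as amplitude recovery to" above 50% of the starting amplitude. Neither document gives a latency criterion for recovery.

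Recovery matters in two places. Under Study Design it is a recorded item: "occurrence of adverse EMG changes and recovery time or loss of signal (LOS) were recorded intraoperatively in all patients". Under RLN identification it helps decide whether the allocated approach continues. For the lateral arm: "If the adverse EMG changes did not recover after traction release or in case of repeated adverse EMG changes, lateral approach was abandoned". For the cranio-caudal arm: "If the EMG changes did not recover or in case of repeated adverse EMG changes, cranio-caudal approach was abandoned".

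On analysis, the protocol states that "the rate of adverse EMG changes, LOS and morbidity (vocal cord palsy, hypoparathyroidism) were compared between group 1 and 2", and that "The primary endpoint was RLN injury". The SAP names t, Mann-Whitney and chi-square tests followed by logistic regression. It does not mention recovery.

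**The concern.** An event that starts on either of two parameters but ends on only one looks like a definitional error. If amplitude never fell by half, the recovery condition already holds at onset, however long latency stays raised. A combined event likewise counts as recovered once amplitude returns, even with latency still prolonged.

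Two things would be at stake. First, recovery times of zero, or undefined ones, would enter the data and make recovery look faster and more frequent than it was. Second, the decision to leave the randomised technique depends partly on non-recovery. If that limb can never apply to latency-only events, conversion for them might rest on the judgement of a surgeon who knows the allocation. Conversion also differs by arm: lateral goes to medial, whereas cranio-caudal goes first to lateral, which is the comparator. A loose trigger could therefore bear on crossover.

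**Working it through.** **1. Is the conflict real?** Write A for amplitude as a percentage of baseline and L for the percentage rise in latency. An event is adverse if A ≤ 50 or L ≥ 10. It is recovered if A > 50. Take whole-number states with A from 0 to 120 and L from −5 to 40, and count those that are adverse and recovered at once.

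| Event type | States | Also meet the recovery rule |
|---|---|---|
| Amplitude only (A ≤ 50, L < 10) | 51 × 15 = 765 | 0 |
| Both parameters (A ≤ 50, L ≥ 10) | 51 × 31 = 1581 | 0 |
| Latency only (A > 50, L ≥ 10) | 70 × 31 = 2170 | 2170 |

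The amplitude limits are exact complements, so the whole conflict comes from the absence of a latency criterion. For example, A = 95 with L = 15 is adverse and recovered together. So is a combined event that has returned to A = 60 with L still at 15. These counts describe the definitions. They are not frequencies of events in patients.

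**2. How large could the effect on a recovery rate be?** The documents give no event counts, so every input here is assumed. Let f be the share of adverse events that are latency-only, 60% the recovery rate among the others, and r the true recovery rate of latency-only events.

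- Reported rate = (1 − f) × 0.60 + f
- True rate = (1 − f) × 0.60 + f × r
- Overstatement = f × (1 − r)

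| f | Reported | True if r = 0 | Overstatement, r = 0 | r = 0.60 | r = 1 |
|---|---|---|---|---|---|
| 10% | 64% | 54% | 10 points | 4 | 0 |
| 30% | 72% | 42% | 30 points | 12 | 0 |
| 50% | 80% | 30% | 50 points | 20 | 0 |

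If latency-only events were coded as zero minutes, the mean recovery time over all events would be (1 − f) times the mean over the other events: 0.90, 0.70 and 0.50 for the same f.

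**3. Which planned results use recovery?**

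| Quantity | Defined through recovery? |
|---|---|
| RLN injury (primary) | No, as stated |
| Effect of adverse EMG changes on injury (secondary) | No, it uses occurrence |
| Rate of adverse EMG changes | No |
| Loss of signal (amplitude under 100 µV) | No |
| Vocal cord palsy, hypoparathyroidism | No |
| Recovery time | Recorded; not named in any comparison or in the SAP |

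The rule for stopping before the second side applies after loss of signal and is set on amplitude, so latency-only events do not reach it.

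**4. Does the conversion rule fail?** It has two limbs in each arm: non-recovery, or repeated adverse changes. Only the first is empty for latency-only events. The recovery definition and both limbs are common to the two arms. Conversion also did not move patients between analysis groups. The randomised numbers less the stated exclusions for monitoring or baseline amplitude are 121 − 9 = 112 and 112 − 26 = 86, which are exactly the analysed groups (112 + 86 = 198).

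**The case for a change.** The best argument for a change is that the allocated technique is the thing under test and recovery helps decide when it is abandoned. Cranio-caudal conversions go to the comparator technique, so a vague trigger could blur the contrast. The word repeated is also unclear when latency never settles: is that one continuing event or a second one? The answer could alter event counts, and adverse changes are both a between-group comparison and a secondary-endpoint factor. The remedy would cost little.

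Part of this stands. The text does not say what recovery means for latency-only or combined events, and a reader of any recovery result would need to know. The rest is weaker. Taken literally, the rule is determinate: the event counts as recovered and the allocated approach continues unless changes repeat. Taken less literally, a return of amplitude presupposes a fall, and the RLN identification section speaks of the EMG changes as a whole recovering, so surgeons may have waited for latency too. The documents do not show which was done, and neither reading creates a difference in the rule between arms. The counting question matters only if episodes are counted. A chi-square test of proportions, as the SAP plans, suggests present or absent per nerve or per patient, and that is unaffected.

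The suggested remedy also assumes that event type was kept. The recorded items listed are latency before and after surgery, occurrence of adverse changes and recovery time. Event type is not among them.

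**Conclusion.** The definitions do not match on their literal text, but the mismatch reaches no result that the plan says it will produce. The possible overstatement of 0 to 50 percentage points rests on assumed shares of latency-only events and assumed true recovery, for a rate that is not a planned output. Any influence on RLN injury is indirect, through the technique used to finish the dissection, and its size cannot be judged from the documents. Both documents are dated March 2020, after referrals from June 2018 to November 2019, and the protocol already reports the analysed patients, so rewording would not change how anyone was operated on.

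This is a missing detail that a sensible analyst handles when writing up. If recovery rate or time is reported, it should be described as amplitude recovery, with a statement of how latency-only and combined events were coded. The event and recovery definitions, and the conversion rules that use them, are for the investigators to reconcile in that description. I take no view on which clinical criterion is right. The conclusion assumes that recovery stays outside the reported comparisons and that the adverse-change rate is an any-or-none proportion. If either proved untrue, the point would deserve another look.
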